Exercise as a buffer against stress induced overeating
ClinicalTrials.gov #: NCT02936076

Study Protocol
10.11.17

Study overview: Subjects will be recruited to participate in this study via advertisements in local newspapers, internet postings, and community newsletters. Interested individuals will be screened via the telephone to determine initial eligibility (see full eligibility criteria below). If deemed eligible via the phone screen, participants will be invited to an orientation session where they will learn additional details about the study, sign an informed consent document, and complete baseline assessment measures. Participants will then be randomized to a 12-week exercise training program or a delayed exercise condition (see below for more details). Assessments will take place at baseline and 12 weeks. Participants will not be compensated for the baseline assessment visit. At 12 weeks, they will be compensated \$25 for completing study questionnaires, a food choice computer task, and measures of weight, fitness and body composition. Further, at baseline and 12 weeks, participants will be asked to respond to prompts via their smartphone 5x/day over a 14-day period while also wearing an armband that objectively measures physical activity. At week 12, participants will receive \$0.50 for each EMA prompt responded to within 45 minutes and a completer's bonus of \$30 if they have >80% compliance and wore the armband for at least 9 days for ≥ 10 hours/day.

Eligibility criteria: To be eligible for the study, participants must be female, aged 18-60, have a BMI of 25 to 40 kg/m^2 , own a smartphone, and be willing to receive and respond to text message prompts for 14 days at baseline and 12 weeks. Exclusionary criteria include: shift workers, those who do not endorse stress-eating, recent weight loss or current enrollment in a weight loss program, women who are pregnant, those with any medical condition that would limit participation in physical activity, diabetes, or an inability to walk without an assisted device or inability to meet exercise recommendations. Participants with a previous history of heart disease or hypertension will be required to provide physician consent prior to participating in this study. Further, individuals with <80% compliance to the EMA monitoring at baseline or those with poor compliance to wearing the armband will not be eligible to participate.

Treatment conditions:

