In-person visit: Height will be assessed at baseline and weight and body composition will be assessed at baseline and 12 weeks. Body composition will be assessed via bioelectrical impedance analysis (RJL Systems Quantum II impedance machine). Participants will be asked to fast for 4 hours, refrain from alcohol for at least 12 hours, and to refrain from strenuous exercise or sauna for 8 hours prior to these measures. As part of these assessment visits, participants will also be given a series of questionnaires (see measures below), be equipped with an armband (used to measure physical activity), and will be instructed on how to respond to the EMA prompts over the 14-day EMA period.

EMA protocol: Participants will be asked to carry their smartphone for 14 days at baseline and 14 days at the end of the intervention. They will report on their stress, mood, hunger, physical activity, overeating episodes, and dietary temptations/lapses as they occur in their natural environment. All entries will be made in response to 5 semi-random prompts delivered throughout the day (between 8:00am and 10:00pm) via text message. Upon receiving the text message, participants will have 45 minutes to click on the link provided and this will direct them to an online questionnaire. Each set of questions will take 3-5 minutes to complete and individuals <80% compliant at baseline will be ineligible to participate in the study.

Sensewear Armband: Participants will wear a Sensewear armband (Body Media, Pittsburgh, PA) for 14 consecutive days (to coincide with the EMA monitoring period) at baseline and 12 weeks. This device is worn on the upper arm and provides valid and reliable estimates of exercise intensity and energy expenditure via a unique combination of sensors (accelerometer, galvanic skin response, heat flux, and skin temperature). Structured exercise bouts (≥ 10 minutes of activity ≥ 3 metabolic equivalents) will be identified and total daily energy expenditure will be computed to examine whether these variables influence stress levels or overeating episodes. Participants in the exercise condition will also be asked to wear this armband during all exercise sessions as these data will be used to confirm participants self-reported physical activity over the 12-week intervention period.

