Exercise as a buffer against stress induced overeating
ClinicalTrials.gov #: NCT02936076

Statistical Analysis Plan
9.11.19

Primary Aim: To compare exercise and delayed exercise conditions on stress-induced overeating (measured via smartphone surveys) at 12 weeks.

Analysis plan: Effects of exercise vs. delayed exercise on stress-induced overeating was examined using a longitudinal regression model implemented with Generalized Estimating Equations (GEE's) with robust standard errors. GEE's using a logit link and further adjusted error terms for the clustered nature of the data. Models included specifications of time (a time-varying indicator of day, indexed by monitoring period).

Secondary Aim 1: To compare exercise and delayed exercise conditions on changes in body weight from baseline to 12 weeks.

Analysis plan: Percent weight loss from baseline to 12 weeks was calculated for each participant and independent samples t-test were used to examine whether exercise and delayed exercise conditions differed from one another.

Secondary Aim 2: To compare exercise and delayed exercise conditions on their self-reported perceived stress at 12 weeks.

Analysis plan: A univariate ANOVA, controlling for baseline stress levels was used to assess whether exercise and delayed exercise conditions differed from one another at 12 weeks.

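### The primary GEE states no time-of-day term, which could bias a between-arm comparison of the stress-overeating relation if exercise shifts the hours of stress

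*SAP*

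**What the plan says.** The SAP's Primary Aim is "To compare exercise and delayed exercise conditions on stress-induced overeating (measured via smartphone surveys) at 12 weeks". Its analysis plan gives a longitudinal regression by GEE with robust standard errors, and adds: "GEE's using a logit link and further adjusted error terms for the clustered nature of the data". On time it says only: "Models included specifications of time (a time-varying indicator of day, indexed by monitoring period".

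The protocol's EMA section states: "All entries will be made in response to 5 semi-random prompts delivered throughout the day (between 8:00am and 10:00pm) via text message". On content it says: "They will report on their stress, mood, hunger, physical activity, overeating episodes, and dietary temptations/lapses as they occur in their natural environment". Stress and overeating are therefore both recorded at the level of the single prompt. On answering, "participants will have 45 minutes to click on the link provided".

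Neither document names hour, prompt slot or time of day as a covariate, stratum or sensitivity analysis. The SAP does not define stress-induced overeating as a variable, and it writes out neither a stress term nor a stress x condition term.

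**The concern.** The prompts span 14 hours, and the model has a stated term for differences between days but none for differences within a day. Stress and overeating may each follow the clock, for example stress in working hours and overeating in the evening. An estimated stress-overeating relation that ignores the hour then mixes the effect of stress with that of the time of day.

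Randomisation balances the scheduled prompts. It does not fix when women are stressed or when they answer at week 12, because both arise after randomisation and an exercise programme can change the daily routine. A shift in the hours of stress in one arm can change that arm's estimated relation even if the relation at every hour is the same. Neither a day term nor the baseline monitoring period removes a shift that arises later. The study asks whether exercise buffers against stress-induced overeating, so an artefact of this kind could look like buffering or hide it.

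**Working it through.** **Inputs from the documents.** Five prompts a day for 14 days (5 x 14 = 70 per woman per monitoring period), spread over 14 hours; a logit GEE; day by monitoring period as the only stated time term. The documents give no event rate, daily pattern, effect size or sample size for this aim, so there is no figure of the plan's own to reproduce.

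**Assumed inputs.** Four daytime slots and one evening slot. Unstressed overeating 5% by day and 16% in the evening (10% as a milder case). Stress at 40% of daytime and 20% of evening prompts. True stress odds ratio (OR) 1.8 at every hour in both arms, so the true ratio of ORs is 1.00.

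**Formula.** Stressed risk in a slot: odds = 1.8 x p/(1 - p).
- Day: 1.8 x 0.05/0.95 = 0.0947, risk 0.0865.
- Evening at 16%: 1.8 x 0.16/0.84 = 0.3429, risk 0.2553.

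The hour is then ignored by pooling slots within stressed and within unstressed prompts.

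**Control arm (evening 16%).**
- Stressed: (4 x 0.40 x 0.0865 + 0.20 x 0.2553)/(1.6 + 0.2) = 0.1895/1.8 = 0.1053
- Unstressed: (4 x 0.60 x 0.05 + 0.80 x 0.16)/(2.4 + 0.8) = 0.248/3.2 = 0.0775
- Pooled OR: (0.1053/0.8947)/(0.0775/0.9225) = 1.40, against a true 1.8

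**Exercise arm, evening stress 20% to 10%.**
- Stressed: 0.1640/1.7 = 0.0965; unstressed: 0.264/3.3 = 0.0800; OR 1.228
- Ratio: 1.228/1.401 = 0.88 (apparent buffering)

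**Exercise arm, daytime stress 40% to 30%.**
- Stressed: 0.1549/1.4 = 0.1106; unstressed: 0.268/3.6 = 0.0744; OR 1.547
- Ratio: 1.547/1.401 = 1.10 (the opposite direction)

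Ratio of ORs (exercise/control) when the truth is 1.00:

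| Stress in the exercise arm | Evening overeating 10% | Evening overeating 16% |
|---|---|---|
| Same as control at every hour | 1.00 | 1.00 |
| Evening 20% to 15% | 0.97 | 0.94 |
| Evening 20% to 10% | 0.93 | 0.88 |
| Daytime 40% to 30% | 1.05 | 1.10 |
| All hours cut by 10% | 1.01 | 1.01 |
| All hours cut by 25% | 1.01 | 1.03 |
| All hours cut by 50% | 1.03 | 1.05 |

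If overeating has no daily pattern (5% in all slots), every ratio is exactly 1.00.

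**Answering route.** Let evening response fall from 85% to 70% in the exercise arm only. The overall overeating risk is 0.0646 in a daytime slot and 0.1791 in the evening slot.
- Control: (4 x 0.0646 + 0.1791)/5 = 0.0875
- Exercise: (4 x 0.85 x 0.0646 + 0.70 x 0.1791)/(3.4 + 0.7) = 0.0842
- OR 0.96; with evening overeating at 10%, 0.98

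These figures count all overeating. Counting only overeating at stressed prompts gives 0.0379 and 0.0374, an OR of 0.99 (1.00 in the milder case).

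**Cross-check with a different daily pattern.** Here stress rises from 15% to 45% over five blocks, the true OR is 2.0 in both arms, and the latest-versus-earliest overeating OR is 1.5 to 5. With no shift, the ratio is 1.00, although the stress OR itself is inflated to 2.15-2.58 in both arms. If exercise flattens the stress profile, the ratio is 0.75 to 0.93. If a flat profile becomes late-weighted, it is 1.08 to 1.33.

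A GEE with arm, period, stress and their interactions was also simulated under no buffering, with 25 or 50 women per arm and 150 replicates. With no shift, it rejected at 5% in 4%-7% of runs. With a flattened or fully reversed profile, it rejected in 14%-53%. With block indicators added, the mean ratio was 0.96-1.01 and rejection 3%-7% in all ten cells completed. Monte Carlo error is about 2 points near 5% and 4 points near 50%.

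**The case against.** The strongest objection is that the larger bias needs a model the SAP does not write. The ratios of ORs have meaning only if a prompt-level stress x condition term is the primary test. If stress-induced overeating is itself a yes/no outcome, no such term exists. A change in how often stress eating happens, including one caused by fewer stressful evenings, is then part of the effect of exercise. This stands, and it makes the point conditional.

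Second, the sizes are wholly assumed. The ratio of 0.88 needs a threefold evening overeating rate and a halving of evening stress with no daytime change. Milder or proportional shifts give 0.93 to 1.05. The high false-positive rates come from large assumed reshaping of the stress profile. The two calculations assume opposite daily patterns, so the direction cannot be predicted either. With no sample size stated, the bias cannot be set against the standard error. All of this stands.

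Third, it can be argued that adjusting for hour changes the estimand. This does not stand for prompt slot: the slot is set by the prompt schedule, not by exercise, so adjusting for it does not remove a treatment effect.

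Fourth, the SAP's list of model terms may not be exhaustive. That is possible, but no other covariate is named for the primary model.

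A reader might infer that the primary comparison is confounded, or that a buffering result would be an artefact. The documents do not support that. They show no daily pattern, no shift in timing between arms and no written stress x condition test.

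**Conclusion.** The point holds in a conditional form. The only stated time term is day by monitoring period, while entries come from five prompts over 14 hours. Two conditions are needed for the main bias: the primary test compares the stress-overeating relation between arms, and exercise changes the hourly pattern of stress. Overeating must also vary by hour. Under the moderate assumptions used, the false ratio then lies between about 0.88 and 1.10, in either direction. With the same hourly pattern of stress and answering in both arms, there is no between-arm bias.

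Under the single-indicator reading, only differential answering by hour remains, and it is small. This is a modest, inexpensive improvement to the model, and it ranks behind stating what the primary outcome and contrast are.

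**What to change.** Add prompt slot (1 to 5, or clock-time block) as a categorical covariate in the primary GEE, beside day and monitoring period. If stress enters the model, estimate the stress x condition term with slot adjusted. The SAP is dated 9.11.19 and written in the past tense. If the analysis has already been run, the slot-adjusted model belongs in the report as a sensitivity analysis, with response rates by slot and arm, and not as a pre-specified primary model.

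The cost is one sentence and about four extra parameters (five slots less one), set against up to 70 prompts per woman per period. It relies on prompt times being stored with each entry, which the documents imply but do not state. A weekend term is optional; nothing above depends on it.
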